7.2.1. Rules for Missing Data

By-Visit Endpoints

All by-visit endpoints will be analyzed either as observed data. Missing data will not be imputed and only the observed records will be included.

Adverse Events and Concomitant Medications

When the onset/start date is a partial date, the date will be imputed to determine treatment emergence of adverse events and whether medication is prior or concomitant (or both). The following rules will be applied to impute onset/start date:

- When year and month are present:
 - If year and month are same as the first dose date, then use the first dose date;
 - If year and month are before the first dose date, then use the last day of the year and month;
 - If year and month are after the first dose date, then use the first day of the year and month.
- When only year is present:
 - If year is the same as the first dose date, then use the first dose date;
 - If year is before the first dose date, then use the last day of the year;
 - If year is after the first dose date, then use the first day of the year.
- If date, month, and year are all missing, do not impute.

7.2.2. Visit Windows

Visit windows will be used to associate assessments with a scheduled visit and will be used only for summarizing data by visit. Visit windows for safety and efficacy assessments will be defined as shown in Table 1 and Table 2.

Table 1: Visit Windows for Safety Assessments

Week	Start Day	Target Day	End Day
5	2	33	70
17	71	113	168
33+ Every 16 Weeks	(Week-1) □ 7 – 55	(Week-1) □ 7 + 1	(Week-1) □ 7 + 56
Safety Follow-up	Last Dosing Date	Last Dosing Date + 30	Last Dosing Date + 30

If an assessment is located both in Safety Follow-up and a regular analysis window, it will only be assigned to Safety Follow-up Visit, and will be reported as such.

Table 2: Visit Windows for Efficacy Assessments

Week	Start Day	Target Day	End Day
17	2	113	168
33+ Every 16 Weeks	(Week-1) □ 7 – 55	(Week-1) □ 7 + 1	(Week-1) □ 7 + 56

If more than 1 assessment is within a given visit window, the assessment closest to the target date will be used. If 2 assessments are equally close to the target day, the earlier assessment will be used.

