5.2.1. Visit Windows

At each specified study visit, procedures will be performed according to the schedule of activities ([Appendix 5](#)).

A study visit may be scheduled on any day within a specified study week. For any given day within the study week, the visit window is ± 5 or ± 7 days, a 10- or 14-day period (ie, the 5- or 7-day period before or after the given day).

Drug supplies must be taken into account when scheduling visits during windows. Visits may be split across the window to allow for drug resupply and completion of study procedures.

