5.2.3. Treatment Guidelines

Dosing with blinded study drug should continue until radiographic progression. Investigators are discouraged from obtaining PSA assessments at their local laboratories during the study and from discontinuing a patient's study drug treatment due to PSA rise alone. Initiation of new therapy for prostate cancer (with the exception of cytotoxic chemotherapy, androgen receptor inhibitors, and investigational agents) at the time of radiographic progression will not mandate discontinuation of study drug if the investigator considers continuing study drug to be beneficial.

5.2.4. Week 5

The visit window is ± 5 days. Drug supply must be taken into account if a window is used to schedule the next visit.

Week 5 procedures are listed in [Table 3](#).

Table 3. Week 5 Procedures

Activity / Assessment	Comment														
General Activities															
Brief physical examination	Measure vital signs (temperature, blood pressure, and heart rate). Perform symptom-directed examination.														
Assess ECOG performance status	
  
 ECOG Status Score	Criterion	
   
 0	Normal activity	
 
 1	Symptoms but ambulatory	
 
 2	In bed < 50% of time	
 
 3	In bed > 50% of time	
 
 4	100% bedridden	
 
 5	Dead	
  
 
Source: Based on Oken 1982.¹²
	ECOG Status Score	Criterion	0	Normal activity	1	Symptoms but ambulatory	2	In bed < 50% of time	3	In bed > 50% of time	4	100% bedridden	5	Dead
ECOG Status Score	Criterion														
0	Normal activity														
1	Symptoms but ambulatory														
2	In bed < 50% of time														
3	In bed > 50% of time														
4	100% bedridden														
5	Dead														
Adverse events review	Record any new or ongoing adverse events.														
Concomitant medications review	Record any new medications or changes in ongoing medications.														

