Appendix 5. Study Schedule of Activities

Study Period or Visit	Screening	Treatment			Unscheduled	Safety FU	Long-Term FU
Study Week	-4 to -1	1	5	17 Then Every 16	Varies [1]	Varies [2]	Every 16
Study Day	-28 to -1	1	29	113	na	na	na
Window (Days) [3]	na	na	±5	±5	na	±7	±7
General Activities							
Informed consent and screening number (IXRS) [4]	X						
Medical history	X						
Eligibility criteria	X						
12-Lead electrocardiogram (local read)	X						
Radiographic assessments	X [5]			X [6]	X opt [7]		X [6]
Randomization (IXRS) [8]		X					
Complete physical examination [9]	X					X	
Brief physical examination [10]		X	X	X	X		
ECOG performance status	X	X	X	X	X	X	
BPI-SF, FACT-P, EQ-5D-5L, QLQ-PR25 questionnaires		X		X		X	X [11]

Study Period or Visit	Screening	Treatment			Unscheduled	Safety FU	Long-Term FU
Study Week	-4 to -1	1	5	17 Then Every 16	Varies [1]	Varies [2]	Every 16
Study Day	-28 to -1	1	29	113	na	na	na
Window (Days) [3]	na	na	±5	±5	na	±7	±7
Adverse events review [12]		X	X	X	X	X	
Concomitant medications review	X	X	X	X	X	X	
Study drug dispensing		X		X			
Study drug accountability			X	X		X	
Long-term follow-up assessments [13]							X
Central Laboratory Evaluations [14]							
Hematology, serum chemistry	X	X		X	X	X	
Testosterone	X						
Prostate-specific antigen	X	X		X		X	

Study Period or Visit	Screening	Treatment			Unscheduled	Safety FU	Long-Term FU
Study Week	-4 to -1	1	5	17 Then Every 16	Varies [1]	Varies [2]	Every 16
Study Day	-28 to -1	1	29	113	na	na	na
Window (Days) [3]	na	na	±5	±5	na	±7	±7

1. Anytime necessary to assess or follow-up adverse events, perform scans, at the patient’s request, or per investigator decision.
2. Approximately 30 days after the last dose of study drug. If a new antineoplastic treatment is initiated before 30 days after the last dose of study drug, then safety follow-up will occur immediately before starting the new treatment.
3. Drug supply must be taken into account if a window is used to schedule the next visit. Visits may be split across the window to allow for drug resupply and completion of study procedures.
4. Must obtain informed consent before performing any study-specific procedures.

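### SAP Table 1 sets the week 5 safety target at day 33, against day 29 in the protocol schedule and in the SAP's own window arithmetic

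*SAP*

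**What the plan says.** SAP 7.2.2 uses visit windows to attach assessments to scheduled visits, for by-visit summaries only. Table 1 (safety) gives these values:

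- Week 5: start day 2, target day 33, end day 70.
- Week 17: start day 71, target day 113, end day 168.
- The row "33+ Every 16 Weeks": target (Week − 1) × 7 + 1, start (Week − 1) × 7 − 55, end (Week − 1) × 7 + 56. The multiplication sign is lost in the text version.

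Within a window, "the assessment closest to the target date will be used". For ties: "If 2 assessments are equally close to the target day, the earlier assessment will be used". Nothing in this section prefers the scheduled visit or excludes unscheduled readings.

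Protocol Appendix 5 has the row "Study Day -28 to -1 1 29 113 na na na", which puts week 5 on day 29 and week 17 on day 113. Protocol 5.2.4 says of week 5: "The visit window is ± 5 days". Protocol 5.2.1 is looser: "A study visit may be scheduled on any day within a specified study week".

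The brief physical examination, which includes vital signs, is done at week 5 and at unscheduled visits (Protocol Appendix 5). SAP 9.8.3 summarizes vital signs at each scheduled assessment and plots mean change from baseline by study visit.

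**The concern.** Every other target in Table 1 agrees with the protocol schedule; week 5 alone is four days late. The target does real work, because it decides which record enters the analysis when a man has more than one reading between days 2 and 70. Week 5 is the first scheduled on-treatment blood pressure, and the protocol lists hypertension among the important identified risks of enzalutamide. If the target is wrong, a reading taken on the scheduled day can be dropped from the week 5 summary in favour of one taken up to a week later.

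**Working it through.** **1. Is day 33 a difference in day counting?** No. Both documents count randomization as day 1 and have no day 0.

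**2. Try to reproduce the SAP's figure.** Target = (Week − 1) × 7 + 1:

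| Week | Formula | Result | SAP Table 1 | Protocol Appendix 5 |
|---|---|---|---|---|
| 5 | 4 × 7 + 1 | 29 | 33 | 29 |
| 17 | 16 × 7 + 1 | 113 | 113 | 113 |
| 33 | 32 × 7 + 1 | 225 | by formula | every 16 weeks after week 17 |

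Other routes to 33 also fail. The middle of the window is (2 + 70)/2 = 36. The middle of study week 5 (days 29 to 35) is 32. Counting from first dose, which may be up to 3 days after randomization, makes study day 29 treatment day 26 to 29.

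**3. Check the window boundaries.** The week 33 window starts on 32 × 7 − 55 = day 169, which is the midpoint of the neighbouring targets: (113 + 225)/2 = 169. The week 17 window starts on day 71, and (29 + 113)/2 = 71. With a week 5 target of 33 the midpoint would be (33 + 113)/2 = 73. The boundary fits 29 and does not fit 33.

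**4. Effect on a reading taken on day 29.** Under target 33 its distance is 4. Readings on days 30 to 36 are at distance 3 or less and replace it. Day 37 ties, and the earlier record (day 29) is kept. Under target 29 its distance is 0 and nothing can replace it.

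**5. Effect over the protocol's ±5-day window.** Take each scheduled day from 24 to 34 (11 days) and pair it with a second reading on any other day from 2 to 70 (68 days), giving 11 × 68 = 748 pairs. Select the record under each target, taking the earlier on a tie, and count the pairs where the selection differs.

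| Scheduled day | Target 33 moves selection away from the scheduled record | Target 33 moves selection toward it |
|---|---|---|
| 24 to 28 (each) | 8 | 0 |
| 29 | 7 | 0 |
| 30 | 5 | 2 |
| 31 | 3 | 4 |
| 32 | 1 | 6 |
| 33 and 34 (each) | 0 | 8 |
| **Total** | 5 × 8 + 7 + 5 + 3 + 1 = **56** | 2 + 4 + 6 + 2 × 8 = **28** |

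Changed pairs: 56 + 28 = 84 of 748 (11%). By position of the second reading, days 24 to 34 give 28 changes each way, days 35 to 42 give 28 away and none toward, and days 2 to 23 or 43 to 70 give none.

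**6. Same count under the looser visit rule.** If a visit may fall on any day of study week 5, with ±5 days around it, scheduled days run from 24 to 40. There are then 17 × 68 = 1156 pairs and 132 changes: 56 away from the scheduled record and 76 toward it.

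These are counts of day combinations with equal weight, not estimates of how many men are affected. The documents give no distribution of visit days and no frequency of unscheduled visits.

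**The case against.** The best defence of day 33 is that it is an acceptable week 5 day. It lies inside study week 5 (days 29 to 35) and inside day 29 ± 5, and under Protocol 5.2.1 the permitted days run from 24 to 40. The middle of that range is 32, which is nearer to 33 than to 29. If visits were spread evenly over those days, target 33 would keep the scheduled record more often than it loses it (step 6). This defeats any claim of harm in one direction. It does not rescue the figure: every other target is the first day of its study week, and the SAP's formula, its boundary and Appendix 5 all point to 29.

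A reader might infer that the error biases the week 5 blood pressure summary, since unscheduled visits may be prompted by adverse events. If second readings are restricted to days 35 to 42, 28 of 88 pairs change, all away from the scheduled record. That pattern belongs to that block of days. Over the full window the changes go both ways, and the documents give no data on when or why second readings occur.

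It can also be said that SAP 9.8.3 speaks of scheduled assessments, so unscheduled readings might never enter the summary. That reading is possible, but 7.2.2 assigns assessments by window without excluding them, so replacement remains possible as the text stands.

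Finally, target 29 does not remove replacement altogether. A scheduled reading on day 24 would still lose to one on days 25 to 33, compared with days 25 to 41 under target 33.

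**Conclusion.** The week 5 target in SAP Table 1 is wrong as written: 33 should be 29, a four-day error in an operative selection rule. The inconsistency follows directly from the documents. The consequence is minor. It needs a man with at least two vital-sign readings in days 2 to 70, close enough together for the target to decide between them, and no consistent direction of bias is shown.

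The reach is the week 5 point of the descriptive vital-sign summary and plot. Efficacy has its own windows with no week 5 row. Hypertension adverse events and the absolute or most-extreme vital-sign criteria do not depend on the target, and no laboratory test is scheduled at week 5. This takes SAP 7.2.2 at its word that windows serve by-visit summaries only, so that the criteria based on two consecutive visits in SAP Table 7 are also unaffected.

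**What to change.** In SAP Table 1, change the week 5 target day from 33 to 29, and make the same change in the windowing program. The start and end days (2 and 70) already fit 29 and can stay. The cost is one number in the document and one in the code. If the week 5 vital-sign table and plot have already been produced with target 33, rerun them.

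If the sponsor also wants scheduled readings kept whenever they exist, that needs a separate sentence giving the scheduled visit precedence within a window. Correcting the target alone does not achieve it.

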8. TIMING OF ANALYSES

The single MFS analyses will be performed after approximately 440 MFS events occur. All secondary endpoints will be evaluated at this time. This will include the single analysis of time to PSA progression and time to first use of new antineoplastic therapy as well as the first interim analysis of overall survival. Approximately 135 death, 500 PSA progression, and 360 new antineoplastic therapy events are expected at the time of this analysis.

Two additional interim analyses and the final analysis of overall survival are planned after approximately 285, 440, and 596 deaths occur, respectively. Additional analyses of the primary or other secondary endpoints are not planned. A multiplicity adjusted inferential procedure will be used to maintain the family-wise 2-sided type I error rate at 0.05. Details on Type I error rate control methodology for the interim and final overall survival analyses are provided in [Section 9.7.1](#) and [Section 9.7.3](#). If an interim OS analysis is statistically significant, it will be reported as the final analysis and no subsequent analyses will be performed.

9. STATISTICAL METHODS

Efficacy analyses will be conducted using the ITT population. Efficacy data will be analyzed according to treatment assignment at randomization. Safety analyses will be conducted using the safety population according to the treatment actually received.

9.1. Patient Disposition

Patient disposition will be summarized by randomized treatment group as follows:

- Randomized patients by randomization stratification factors;
- Patients in the ITT, and safety populations and the reason for exclusion from 1 or more populations;
- Patients in the treatment and long-term follow-up periods;
- Patients discontinuing treatment and the reasons for discontinuation;
- Patients withdrawing from long-term follow-up and the reasons for withdrawal.

The following listings will be produced:

- Patients who received treatment different from the treatment randomized;
- Patients discontinuing from each study period after enrollment.

9.2. Protocol Deviations

Patients with major protocol deviations will be listed and summarized by treatment group as randomized. Categories of major deviations are as follows:

- Eligibility criteria were not met;
- Developed criteria for discontinuation of study drug but did not discontinue study drug treatment;
- Received excluded concomitant medication;
- Received the wrong treatment or incorrect dose;
- Were incorrectly stratified
- Did not sign informed consent or study-specific procedures were performed before informed consent was signed.

A detailed list of all major protocol deviations will be determined before the study is unblinded and a listing of all major deviations will be provided.

9.3. Demographics and Baseline Characteristics

The following demographic and baseline characteristics will be summarized by treatment group for all patients in the ITT population and by geographic region:

- Age, race, weight, and body mass index;
- Geographic region (North America, European Union, rest of world);
- Categorized PSA doubling time (< 6 months, ≥ 6 months);
- Baseline use of a bone targeting agent (yes, no);
- Eastern Cooperative Oncology Group (ECOG) performance status;
- Serum PSA;
- PSA doubling time (continuous);
- Quality of life (EQ-5D-5L health score and FACT-P global score);
- Selected laboratory parameters including: testosterone, absolute neutrophil count, platelet count, hemoglobin, total bilirubin, alanine aminotransferase (ALT), aspartate aminotransferase (AST);
- History of cardiovascular disease as defined in Appendix 2.

Listings will be provided for these parameters for all randomized patients.

9.4. Disease Characteristics and Previous Therapies

The following medical history and disease characteristics will be summarized by treatment group as randomized for all patients in the ITT population:

- Time (months) from initial pathological diagnosis or first treatment for prostate cancer to randomization, whichever is earlier;
- Total Gleason score category at diagnosis (Low [2–4], Medium [5–7], and High [8–10]);

Previous therapies for prostate cancer will be summarized by treatment group as randomized for all patients in the ITT population as follows:

- Number of prior prostate cancer therapies;
- Number of prior hormonal therapies;
- Prior nonhormonal therapy use (yes/no);
- Use of bisphosphonate or denosumab therapy (yes/no) at baseline;
- History of surgical prostate cancer procedures (yes/no);
- Type of surgical procedures (prostatectomy, orchiectomy, transurethral resection of the prostate [TURP], cryoablation, and other).

9.5. Extent of Exposure and Compliance of Study Drug

Data from patients in the safety population will be used to summarize the extent of exposure, compliance, and dose modification of study drug by treatment group as treated.

Treatment duration, total number of capsules taken, and percent overall compliance rate will be calculated and summarized by treatment group as treated. Treatment duration will be calculated as (date of last dose of study drug – date of first dose of study drug + 1). For patients who are continuing study drug at the analysis cutoff date, the last known date of study drug taken will be used as date of last dose of study drug. Treatment duration will be summarized both as a continuous measure and a categorical measure (≤ 3 months, 3 to < 6 months, 6 to < 12 months, ≥ 12 months). Number of capsules taken will be calculated based on the number of capsules dispensed at all study visits minus the number of capsules indicated as returned. The total cumulative dose in milligrams (mg) will be calculated as (40 mg \times number of capsules taken), as each capsule is equivalent to 40 mg of the study drug or placebo.

Percent overall compliance rate will be defined as the number of capsules taken during the study divided by the expected number of capsules, multiplied by 100. Capsules from bottles not returned will be subtracted from the number of capsules taken and the expected number of capsules in calculating percent overall compliance rate. Each patient will be taking 4 capsules each day while on study treatment. A patient's expected number of capsules will

be calculated as $[4 \times (\text{date of last dose prior to data cutoff date} - \text{date of first dose of study drug} + 1)]$. However, for subjects who have dose modifications (eg, dose reduction or dose withholding), the expected number of capsules will be calculated according to the dose modification. Percent overall compliance will be summarized both as a continuous measure and a categorical measure in increments of 20%.

Patients with at least 1 dose modification (including dose reduction and dose withholding) and the reason for the dose modifications will be summarized by treatment group as treated.

A data listing will be provided to present dose administration, modifications, and the derived compliance variables.

9.6. Concomitant Medications

Concomitant medications taken during the study treatment period will be summarized for all patients in the safety population by treatment group as treated. Medications are considered concomitant if exposure occurs during the treatment-emergent period.

Subsequent therapies taken after study drug discontinuation will be summarized by treatment group and overall. In addition, subsequent antineoplastic therapies will be summarized separately by treatment group.

All medications recorded on the case report form will be listed.

[figure not shown]
9.7. Efficacy Analyses

The single MFS analysis will be performed after approximately 440 MFS events occur. All secondary endpoints will be evaluated for efficacy at this time. This will include the single analysis of time to PSA progression and time to first use of new antineoplastic therapy as well as the first interim analysis of overall survival. Approximately 135 death, 500 PSA progression and 360 new antineoplastic therapy events are expected at the time of this analysis. Two additional interim analyses and the final analysis of overall survival are planned after approximately 285, 440, and 596 death events occur, respectively. No additional analyses of other efficacy endpoints are planned at the time of the additional interim and final analyses of overall survival. If an interim analysis of overall survival is statistically significant, it will be reported as the final analysis and no subsequent analyses will be performed.

9.7.1. Multiplicity Adjustment for Efficacy Analysis

Adjustment for multiplicity will be considered for MFS based on ICR assessment, time to PSA progression, time to first use of new antineoplastic therapy, and OS. All secondary endpoint analyses will be performed at the time of the single MFS analysis. To maintain the family-wise 2-sided type I error rate at 0.05, a parallel testing strategy between overall survival (with allocated type I error rate 0.03) and remaining key secondary endpoints (time to PSA progression and time to first use of new antineoplastic therapy with allocated type I error rate 0.02) will be performed. Testing strategy for primary and key secondary endpoints is summarized in [Figure 1](#).

Figure 1. Testing Strategy for Primary and Key Secondary Endpoints

MFS, metastasis-free survival; OS, overall survival; TTPSA, time to prostate-specific antigen progression; TTFAnti, time to first use of new antineoplastic therapy.

** Overall survival will be tested at 0.05 only if both time to PSA progression and time to new antineoplastic therapy endpoints are significant.*

Details of primary and key secondary endpoints testing as a step-by-step approach will be as follows:

1. Compute p-value for MFS. If p-value < 0.05, declare statistical significance for MFS and go to step 2 below. Otherwise stop.
2. Compute p-value for time to PSA progression. If p-value < 0.02, declare statistical significance for time to PSA progression and go to step 3 below. Otherwise declare time to PSA progression failed to show significance, continue with step 4 below and test OS at significance level 0.03.
3. Compute p-value for time to first use of new antineoplastic therapy. If p-value < 0.02, declare statistical significance for time to first use of new antineoplastic therapy, continue with step 4 below and test OS at significance level 0.05. Otherwise, declare time to first use of new antineoplastic therapy failed to show significance, continue with step 4 below and test OS at significance level 0.03.

4. Compare OS with group sequential testing methodology based on 3 interim analyses and 1 final analysis (described in [Section 9.7.3](#)) at a significance level of 0.05 (if both time to PSA progression in step 2 and time to new antineoplastic therapy in step 3 are declared significant) or 0.03 (if either time to PSA progression in step 2 or time to new antineoplastic therapy in step 3 failed to show significance). The O'Brien-Fleming alpha spending function will be used to determine the stopping boundaries based on the number of events observed at the interim looks to control the overall 2-sided alpha at 0.05 or at 0.03.³

All other efficacy analyses (including sensitivity analyses for primary, and other secondary endpoints) and associated p-values will be deemed exploratory, for which no adjustment for multiplicity will be used.

The key efficacy analyses, order of testing, and multiplicity adjustment rules are summarized in Table 3.

Table 3: Key Efficacy Analyses and Multiplicity Adjustment

Order of Testing	Population	Declare Significant	Statistic	Strata
1. Metastasis-free survival [1]	ITT	p < 0.05	Stratified log-rank test [2]	 PSA doubling time  Prior or current bone targeting agents
	ITT, subgroup [2]	NA		
2. Time to PSA progression	ITT	p < 0.02	Stratified log-rank test	
3. Time to first use of new antineoplastic therapy	ITT	p < 0.02	Stratified log-rank test	
4. Overall survival [3]	ITT	p < 0.05 or p < 0.03 [4]	Stratified log-rank test	

ITT: intent-to-treat; NA: not applicable; PSA: prostate-specific antigen.

1. MFS is the primary analysis.
2. The MFS subgroup analysis will be performed with an unstratified log-rank test.
3. Three interim analyses and 1 final analysis are planned for OS, details of each analysis are provided in [Section 9.7.3](#).
4. If both time to PSA progression and time to first use of new antineoplastic therapy are declared significant, OS will be tested at a 0.05 significance level; otherwise, OS will be tested at 0.03.

